AE = adverse event; DHA=Directions for Handling and Administration; ED = exposure day; EOT = end of treatment; EPD = electronic patient diary; ET = Early Termination; F8 = target gene for hemophilia A; FVIII = coagulation factor VIII; HIV = human immunodeficiency virus; ICF = informed consent form; rFVIII Fc = recombinant coagulation factor VIII Fc fusion protein; SAE = serious adverse event.

- a For subjects on episodic treatment who have had no infusions of factor since the previous visit, blood draws will only be required every 24 weeks, rather than every 12 weeks.
- b If an investigator chooses to have the subject temporarily withdraw from treatment with rFVIII Fc and delay the start of ITI, the subject should continue to participate in Interim visits every 12 ± 2 weeks (per the prophylaxis regimen).
- c A follow-up telephone call or in-person visit is required 7 to 14 days after the last dose of rFVIII Fc to monitor AEs, SAEs, and concomitant medications and procedures.
- d Vital signs include blood pressure, pulse rate, respiratory rate, and temperature (°C). Assessments for in-clinic injections should be taken prior to and approximately 20 minutes after the end of the rFVIII Fc injection.
- e Health outcome assessments will be performed every other visit during episodic and prophylaxis regimens, that is, every 24 weeks.
- f Hematology includes white blood cell count and differential, red blood cell, hemoglobin, hematocrit, and platelet count.
- g Blood chemistry includes sodium, potassium, chloride, total protein, total bilirubin, gamma glutamyl transferase, aspartate aminotransferase, alanine aminotransferase, alkaline phosphatase, blood urea nitrogen, serum creatinine, and glucose.
- h An unscheduled visit may be required to repeat inhibitor testing under this protocol if the ET/EOT Visit inhibitor test is not evaluable or to obtain a sample to confirm a positive inhibitor test result.

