#### **10.2.5.2.3. Use of Bypassing Agents**

Subjects with confirmed or suspected inhibitors may receive bypassing agents (aPCC [FEIBA] or rFVIIa [NovoSeven]) at the discretion of the Investigator and within labeled dosing recommendations for the specific bypassing agent. The Investigator may prescribe bypassing agents for active bleeding or if there is a high clinical suspicion of bleeding or potential for bleeding. When possible, bleeding should be confirmed via physical examination and/or imaging prior to administration of a bypassing agent; Confirmation of bleeding should not cause any unnecessary delay in the start of treatment, as judged by the Investigator. In the event of an emergency, prior consultation with the Investigator is not required before administration of a bypassing agent; however, the Investigator must be notified of such use.

In subjects with low-titer inhibitors, bleeding events may be controlled with increased doses of replacement FVIII to overwhelm the inhibitor by antigen excess. In subjects with high-titer inhibitors, bleeding may be treated with bypassing agents, which can bypass FVIII inhibition. During the study, the Investigator will determine if increased doses of replacement FVIII or use of bypassing agents is appropriate.

During ITI treatment, subjects may also receive bypassing agents as needed for active bleeding or if there is a high clinical suspicion of bleeding or potential for bleeding. The use of bypassing agents in the setting of ITI requires awareness of FVIII activity levels and close monitoring for cessation of bleeding events.

It is recommended that Investigators discontinue the use of bypassing agents once the inhibitor titer is  $< 0.6$  BU/mL (negative titer, or values considered negative per local laboratory reference) or once rFVIII-Fc provides sufficient hemostatic control, as judged by the Investigator.

The prophylactic use of bypassing agents in subjects with confirmed or suspected inhibitors must be communicated to the Sponsor Medical Monitor with documentation of rationale.

All use of bypassing agents must be documented in the appropriate section of the eCRF.

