### 10.2.7. Immune Tolerance Induction Therapy

Subjects who develop high titer inhibitors as defined in Section 10.2.5.2.2 and choose to remain in the study will undergo ITI with rFVIII Fc, as described below. Subjects with low titer inhibitors as defined in Section 10.2.5.2.1 will be eligible for ITI if the Investigator determines that bleeding is no longer adequately controlled despite increased rFVIII Fc doses or if bypassing agents are required to treat bleeding in a subject with a positive low titer inhibitor (see Section 5.3). Separate consent is required before starting an ITI regimen.

The timing of ITI initiation in patients with a peak inhibitor titer of >10 BU/mL, including patients who experience serious or life-threatening bleeding or have frequent mild to moderate bleeding, will be based on the Investigator's clinical judgement.

If an investigator chooses to have the subject temporarily suspend treatment with rFVIII Fc, and delay the start of ITI, the subject should continue to participate in Interim visits every  $12 \pm 2$  weeks (per the prophylaxis schedule in Section 4.2.2.1).

The ITI regimen will approximate the high-dose treatment arm of the International ITI Study protocol [Hay and DiMichele 2012] and will utilize single injections of rFVIII Fc 200 IU/kg, daily. Concomitant immunomodulation will not be allowed during ITI therapy.

ITI outcomes will be assessed on an ongoing basis as described in Section 10.2.7.4. Additional informed consent must be obtained prior to the ITI assessments beginning at Day 0.

Immune tolerance induction therapy assessments will be performed according to the schedule as described in Section 4.2.2.3.

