5.2.2. End Date and Time of the Last Treatment Regimen

The end of the last treatment regimen will be either:

- The date and time of the last rFVIII Fc dose for patients whose last treatment regimen was prophylaxis, ITI, or if they ended the study in a surgical/rehabilitation period
- At 23:59 on the day of the last non-safety follow-up study visit for patients whose last treatment regimen was episodic.

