5.2.3. Treatment Regimen Changes

In the following sections, new treatment regimen refers to the regimen to which the patient has changed, and the previous treatment regimen refers to the regimen immediately before the new treatment regimen. The start date and time of the new treatment regimen and the end date and time of the previous treatment regimen are defined in the following scenarios:

- From the episodic regimen to a prophylactic regimen: The prophylactic regimen starts at the date and time of the first prophylactic dose in the prophylactic regimen. The episodic regimen ends 1 minute before that. If the time of the first prophylactic dose in the prophylactic regimen is not available, the prophylactic regimen will start at 00:01 on the day of the first prophylactic dose in the prophylactic regimen, and the episodic regimen will end at 23:59 on the day prior to that.
- From the episodic regimen to an ITI regimen: The ITI regimen starts at the date and time of the first ITI dose in the ITI regimen. The episodic regimen ends 1 minute before that. If the time of the first ITI dose in the ITI regimen is not available, the ITI regimen will start at 00:01 on the day of the first ITI dose in the ITI regimen, and the episodic regimen will end at 23:59 on the day prior to that.
- From a prophylactic regimen to the ITI regimen: If there is no prophylactic dose on the day of the treatment regimen change recorded in the eCRF, the ITI regimen starts at 00:01 on the day of treatment regimen change, and the prophylactic regimen ends at 23:59 on the day prior to the day of treatment regimen change. If there is a prophylactic dose on the day of treatment regimen change, the ITI regimen starts 1 minute after that prophylactic dose, and the prophylactic regimen ends on the date and time of that prophylactic dose.
- From a ITI regimen to a prophylactic regimen (tapering): If there is no ITI dose on the day of treatment regimen change recorded in the eCRF, the prophylactic regimen starts at 00:01 on the day of treatment regimen change, and the ITI regimen ends at 23:59 on the day prior to the day of treatment regimen change. If there is an ITI dose on the day of treatment regimen change, the prophylactic regimen starts 1 minute after that dose, and the ITI regimen ends on the date and time of that dose.

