5.4.2. Efficacy Period

The efficacy period will be used for the evaluation of efficacy and health outcome endpoints. For a patient to have an evaluable efficacy period over the duration of study, he must have at least 1 day of treatment for an episodic regimen or at least 2 prophylactic injections for prophylactic regimens.

The start and end, and the total duration of the efficacy period for a given treatment regimen is the same as the start and end, and the total duration of that treatment regimen defined in Section 5.2.4 with the exceptions described in the following two subsections. The start of the efficacy period for each patient is the start of their first treatment regimen and the end is the end of their last.

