5.4.2.2. Adjustments Due to Large Injection Intervals

For analysis purposes, the efficacy period will also be adjusted to account for large intervals between injections resulting from missing data. A large interval is defined as >28 days between any 2 adjacent rFVIIIFc injections within a prophylactic treatment regimen and any such intervals will be removed from the efficacy period. The efficacy period prior to each such interval will end at the time of the first injection of this interval and restart (or start if it is the first interval of a treatment regimen) at the time of the second injection of this interval. The efficacy period will be adjusted for each identified interval that is not within a surgical/rehabilitation period. This algorithm applies only to prophylactic regimens and no adjustment for large injection intervals will be made for episodic treatment regimens.

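### By-regimen ABR and consumption count the days when rFVIIIFc is deliberately suspended before ITI, because SAP 5.2.3 ends prophylaxis at the recorded regimen change and not at the last dose

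*SAP*

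**What the plan says.** Protocol 10.2.7 provides for the case "If an investigator chooses to have the subject temporarily suspend treatment with rFVIII Fc, and delay the start of ITI". It sets no maximum length and keeps the subject on the prophylaxis visit schedule. Protocol 10.2.5.2.3 adds that "Subjects with confirmed or suspected inhibitors may receive bypassing agents", and it foresees prophylactic use of those agents, to be reported to the medical monitor.

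The SAP has no suspended state. For a prophylaxis-to-ITI change with no prophylactic dose on the day recorded in the eCRF, SAP 5.2.3 states that "the prophylactic regimen ends at 23:59 on the day prior to the day of treatment regimen change", and ITI starts at 00:01 on the change day. If there is a prophylactic dose on that day, prophylaxis ends at that dose.

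SAP 5.4.2 says that the efficacy period for a regimen "is the same as the start and end, and the total duration of that treatment regimen defined in Section 5.2.4", subject to the surgery and large-interval adjustments. That period is the denominator for consumption (SAP 6.6.1.4) and ABR (SAP 7.4.3). Both are secondary endpoints and both are tabulated by regimen.

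Two other SAP rules handle the end of prophylaxis differently:
- When prophylaxis is the last regimen, SAP 5.2.2 ends it at "The date and time of the last rFVIII Fc dose for patients whose last treatment regimen was prophylaxis, ITI".
- Before surgery, SAP 5.4.2.1 ends it at the last dose for prophylaxis or bleeding, and expressly does not credit the days from that dose to the surgical period.

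**The concern.** A rate under prophylaxis should be calculated over time on prophylaxis. Here, days on which the drug was withheld on purpose can be added to the denominator while contributing nothing to the dose total. Annualized consumption then reads too low. The ABR either absorbs quiet days, possibly covered by bypassing agents, or counts bleeds that occurred off drug as if they had broken through prophylaxis.

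The rule also treats like subjects differently. A subject who suspends and never starts ITI has prophylaxis closed at the last dose under SAP 5.2.2. A subject who suspends for the same time and then starts ITI can be credited with the whole gap. The SAP gives no reason for the difference.

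**Working it through.** The plan states no figure that depends on this point, so there is nothing to reproduce. The check has two parts.

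**1. Does any rule remove the gap?** The candidate is SAP 5.4.2.2: "A large interval is defined as >28 days between any 2 adjacent rFVIIIFc injections within a prophylactic treatment regimen". Three features of that section matter.
- The pair of injections must lie within a prophylactic regimen. Here the second injection is the first ITI dose.
- Its stated purpose is gaps that result from missing data, not planned suspension.
- It applies only to prophylactic regimens, so it would not clean the ITI denominator if the days fell there.

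Read literally, it does not reach this gap. If a programmer applies it across the boundary anyway, gaps over 28 days drop out and gaps of up to 28 days stay. So gaps of up to 28 days remain under any reading.

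**2. How large is the effect?** The documents give no suspension lengths, times on drug or bleed counts, so all of these are assumed. Let *D* be days on prophylaxis up to the last dose, *w* the gap in days, and *T* the total IU/kg, with no rFVIIIFc given in the gap.

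- Consumption on prophylaxis time: *T*/*D* × 365.25
- Consumption with the gap counted: *T*/(*D*+*w*) × 365.25
- Relative fall: *w*/(*D*+*w*), whatever the dose

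Take *T* = 15 doses × 50 IU/kg = 750 IU/kg, with *D* = 45 (a dose every 3 days) or *D* = 60 (every 4 days). Consumption is in IU/kg per year.

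| Gap *w* | *D* = 45 | Change | *D* = 60 | Change |
|---|---|---|---|---|
| 0 | 750/45 × 365.25 = 6,088 | – | 750/60 × 365.25 = 4,566 | – |
| 14 | 750/59 × 365.25 = 4,643 | −24% | 750/74 × 365.25 = 3,702 | −19% |
| 28 | 750/73 × 365.25 = 3,753 | −38% | 750/88 × 365.25 = 3,113 | −32% |

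Longer time on drug dilutes the effect. With *D* = 120, the falls are 14/134 = 10% and 28/148 = 19%.

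For gaps over 28 days the result depends on the reading of 5.4.2.2. With *D* = 60 and *w* = 84, the fall is 84/144 = 58% if the rule is not applied, and nil if it is.

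For ABR, assume 1 bleed in *D* = 60 days, giving 1/60 × 365.25 = 6.09. With a 28-day gap containing *k* bleeds, ABR = (1+*k*)/88 × 365.25:
- *k* = 0: 4.15
- *k* = 1: 8.30
- *k* = 2: 12.45

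ABR falls when the bleed rate in the gap is below the on-drug rate and rises when it is above.

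**The case against.** The case for leaving the rule alone has several sound parts.

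- **The change date is undefined.** A reader might infer that the off-drug days always go to prophylaxis up to the day before ITI. The documents do not say so. For this transition SAP 5.2.3 uses the change recorded in the eCRF; only for episodic-to-ITI does it use the first ITI dose. If a site records the change when suspension begins, the days go to ITI. They are still misattributed, but to a different regimen.
- **Very large distortions are not established.** A reader might infer falls of 58% or more from multi-month suspensions. These exist only if 5.4.2.2 is not applied. Almost all of the gap lies inside the prophylactic regimen as 5.2.3 defines it, so a programmer could reasonably apply the rule.
- **Not every table is affected.** A reader might infer that the days are labelled prophylaxis throughout. SAP 5.1.1.2 and 5.4.7 build the inhibitor-subgroup tables from the whole efficacy period and, for the inhibitor sub-classification, split it at inhibitor onset; none of these tables divides time by regimen. Protocol 16.2.1 also calls for separate summaries after the last negative inhibitor test. However, the by-regimen tables under SAP 5.1.1.1 carry no such cut, and SAP section 10 does not list this as a change.
- **An undiluted dose summary exists.** SAP 6.6.1.3 derives average weekly prophylactic dose from consecutive prophylactic doses only. It does not repair annualized consumption or ABR.
- **The stakes are modest.** The analyses are descriptive, the endpoints are secondary, medians are reported, and the number of affected subjects is unknown.

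It can also be said that 5.2.3 simply keeps regimens contiguous, and that study end and surgery are different situations. That explains the wording, but it does not justify crediting a planned off-drug interval when 5.4.2.1 refuses credit for the interval before surgery.

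**Conclusion.** The point holds for the by-regimen ABR and annualized consumption tables. A stated rule, not merely missing detail, puts deliberately off-drug days into a regimen's denominator, and it is inconsistent with SAP 5.2.2 and 5.4.2.1. The regimen is prophylaxis if the eCRF change is recorded at ITI start, and ITI if it is recorded at suspension.

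Per affected subject, by-regimen prophylaxis consumption is understated by about 19-24% for a 14-day gap and 32-38% for a 28-day gap. This assumes 45 to 60 days on drug, no rFVIIIFc in the gap, and the change recorded at ITI start. The direction of the ABR error cannot be stated in advance. The effect on a reported mean or median cannot be calculated, because the documents give neither the number nor the length of such pauses. The primary endpoint is not touched.

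**What to change.** In SAP 5.2.3 and 5.4.2, for subjects whose rFVIIIFc is suspended before ITI:

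1. End the prophylactic efficacy period at the last rFVIIIFc dose given for prophylaxis or bleeding, as 5.4.2.1 already does before surgery. Using the last prophylactic dose instead would drop later rFVIIIFc bleed treatments and their bleeds from every regimen.
2. Start the ITI efficacy period at the first ITI dose, as 5.4.8 does for the ITI period. Both ends then rest on dose dates, so the timing of the eCRF entry no longer matters.
3. Exclude the interval between from both regimens' efficacy denominators. Tabulate its days, bleeds and bypassing-agent use separately, and keep it in the safety period.
4. State whether 5.4.2.2 applies across a regimen boundary.

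The cost is a few sentences and one programming rule; dose dates and bypassing-agent use are already collected. By-regimen efficacy time falls slightly, and bleeds in the gap appear in their own table and not in the prophylaxis ABR. If rFVIIIFc is given for a bleed during the suspension, the days before that dose stay in prophylaxis unless 5.4.2.2 removes them. No change to clinical management is involved.

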### 10.2.7.5. Transition to a Prophylactic Regimen Following Immune Tolerance Induction Therapy Success (Tapering Period)

Subjects fulfilling the criteria for complete ITI success will transition (“taper off”) to a prophylactic regimen over a minimum period of 3 months. The duration of the tapering period

CONFIDENTIAL

The information contained herein may not be used, disclosed, or published without the written consent of Bioerativ Therapeutics Inc.

may be modified by the Investigator with the Sponsor's medical monitor's approval based on the subject's clinical response.

The suggested "tapering" schedule is similar to that used on the International ITI Study protocol [Hay and DiMichele 2012]:

[REDACTED]

• [REDACTED]

• [REDACTED]

• [REDACTED]

*Prophylaxis Regimen during Follow-up:* Based on clinical response, adjust the prophylaxis regimen in the range of 25 to 65 IU/kg every 3 to 5 days, utilizing more frequent dosing or doses up to 80 IU/kg, as required.

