3.1.5.3. Immune Tolerance Induction (ITI) Dose Adjustment

An ITI regimen comprises of high daily doses of replacement factor. Therefore regimen in this study approximates the high-dose treatment arm of the International ITI Study protocol, and utilizes single injections of rFVIII Fc of 200 IU/kg/day. After a maximum of 33 months of ITI, the administered dose will be tapered off as follows:

- [REDACTED]
- [REDACTED]

After this tapering period, the patient reverts to a prophylactic treatment regimen for the relapse monitoring period. See Section 7.4.9 for further details.

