5.2.4. Duration of a Treatment Regimen

The duration of a given treatment regimen is the time period from the start of the treatment regimen to the end of that treatment regimen. The duration will stop and start for each treatment

	Statistical Analysis Plan	Final v1.0
---	----------------------------------	-------------------

regimen change. If a patient is treated in a given treatment regimen more than once, the total durations in the same treatment regimen will be added together. For example, if a patient is treated with the prophylactic regimen and then undergoes surgery and then goes back to the prophylactic regimen, then his total duration in the prophylactic regimen will be the sum of the two durations in the prophylactic regimen. Further details will be provided for individual analysis where needed.

The total duration of time allocated to each treatment regimen will be calculated in minutes and converted to days as the number of minutes divided by 1440.

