5.4.4. Safety Period

The overall safety period is defined as beginning at the first dose of study medication rFVIII Fc. For patients who are subsequently enrolled, the safety period ends on the date of the Final Safety Follow-up Visit (by telephone or in person), 7 to 14 days after the last dose of rFVIII Fc. For patients who fail screening, this period ends on the date that this is confirmed.

The safety period on a specific treatment regimen is as described in Section 5.2 except that the end of the patient's last treatment regimen is the end of their safety period.

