7.4.9. Response to Immune Tolerance Induction (ITI)

The ITI Analysis Set will be analyzed for response to the treatment regimen. Possible treatment responses are:

Complete Success

All of the following criteria are met:

1. Negative inhibitor titers in 2 consecutive determinations at least 28 days apart
2. IR $\geq 66\%$ of baseline in 2 consecutive determinations at least 28 days apart
3. $t_{1/2} \geq 6$ hours

Partial Success

The determination of partial success will be made only for patients who have completed 33 months of ITI but who do not fulfill the criteria for complete success. To achieve partial success, the following criteria must be met after patients have completed 33 months of ITI:

- Negative inhibitor titers on 2 consecutive determinations at least 28 days apart AND
- Either of the following (but not both):
 - IR $\geq 66\%$ of baseline in 2 consecutive determinations at least 28 days apart, or
 - $t_{1/2} \geq 6$ hours

Failure:

ITI failure is defined as the inability to meet criteria for Complete Success or Partial Success after 33 months on ITI.

Early Withdrawal/ITI Ongoing:

Patients may withdraw from the study during the ITI period before reaching 33 months or complete or partial success. In addition, any patients still in the ITI sub-study at the time of EoS or interim analysis will be included in this category.

Response categories of complete success, partial success, failure, and early withdrawal will be presented overall for the ITI Analysis Set, and separately for the inhibitor subgroups specified in Section 5.1.2.5, namely:

- Patients with high-titer inhibitors
- Patients with low-titer inhibitors that meet the clinically meaningful criteria
- Patients with high-titer inhibitors or low-titer inhibitors that meet the clinically meaningful criteria

Patients fulfilling the criteria for complete success will transition to a “tapering” regimen over a minimum period of 12 weeks with the aim of starting a prophylactic rFVIII Fc regimen, as described in [Section 10.2.7.5](#) of the protocol, and will be further monitored for relapse for up to 9 months as described in [Section 10.2.7.6](#) of the protocol.

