During this period, the monitoring for relapse is via blood samples processed by the central laboratory using the Nijmegen-modified Bethesda assay for inhibitor detection, as well as IR assessments. The inhibitor titer and IR will be measured every 3 months during the follow up period. rFVIII Fc $t_{1/2}$ assessments will be performed 12 months after ITI success. If any of these tests reverse previously met criteria, at any time between the start of tapering through the beginning of prophylaxis, the tests must be repeated within 2 to 4 weeks to confirm relapse.

Relapse is defined as any of the following, occurring within 12 months following complete ITI success:

- A positive inhibitor (≥ 0.6 BU/mL using the Nijmegen assay) that is confirmed by a second test result of ≥ 0.60 BU/mL from a separate sample, drawn at least 2 weeks following the date that the original sample was drawn.
- 
- $t_{1/2} < 6$ hours.

The incidence of relapse during both the tapering and formal relapse monitoring period, in patients who are complete successes, will also be part of the summary.

A data listing will be generated for all patients in the ITI sub-study. This will include date of first inhibitor sample with a positive result, all inhibitor, IR, and $t_{1/2}$ measurements after commencement of ITI therapy, as well as dosing information. It will also include elapsed time to each assessment and a flag to indicate the patient’s ITI status.

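### SAP 5.2.3 does not clearly assign the post-ITI taper to a regimen; on the plain reading of its label, taper doses count as prophylaxis in the by-regimen tables

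*SAP*

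**What the plan says.** The SAP recognizes three regimens: episodic, prophylactic and ITI (SAP 3.1.2). It has no taper category.

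The rule for leaving ITI is in SAP 5.2.3 and is headed "From a ITI regimen to a prophylactic regimen (tapering". Prophylaxis starts at 00:01 on the change day recorded in the eCRF, or one minute after an ITI dose given that day. ITI ends immediately before, so nothing lies between the two.

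Other sections give a different sequence:

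- SAP 3.1.5.3, after the (redacted) taper schedule: "After this tapering period, the patient reverts to a prophylactic treatment regimen for the relapse monitoring period".
- SAP 7.4.9: complete successes move to a taper "over a minimum period of 12 weeks with the aim of starting a prophylactic rFVIII Fc regimen". SAP 5.1.2.2 has the same order.
- SAP 3.1.2.3 describes the taper under the ITI regimen heading, and SAP 3.1.3 speaks of the tapering period as belonging to the ITI regimen.
- Protocol 10.2.7.5, for the follow-up after the taper: "adjust the prophylaxis regimen in the range of 25 to 65 IU/kg every 3 to 5 days".

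The 5.2.3 boundary feeds the analysis periods:

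- SAP 5.2.4: "The duration of a given treatment regimen is the time period from the start of the treatment regimen to the end of that treatment regimen".
- SAP 5.4.2: "the total duration of the efficacy period for a given treatment regimen is the same as the start and end", with adjustments only for surgery and for injection gaps over 28 days.
- SAP 5.4.4: "The safety period on a specific treatment regimen is as described in Section 5.2", apart from the end of the last regimen.

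SAP 6.6.1.4 derives annualized consumption by regimen and overall, and 7.4.7 tabulates it by regimen.

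**The concern.** Taper time has to fall into one of three regimens, and the SAP points two ways. The label in 5.2.3 suggests that the change from ITI to prophylaxis is the start of the taper. The narrative sections place that change at the end of the taper. The deciding date is whatever the site records as the regimen change, and no section says which day to record.

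If the label is followed, at least 12 weeks of doses stepping down from 200 IU/kg/day are annualized together with ordinary prophylaxis of 25 to 65 IU/kg every 3 to 5 days. By-regimen consumption for prophylaxis would then no longer describe prophylaxis alone. Bleeds and adverse events during the taper would also move to the prophylaxis column, in a direction that cannot be predicted. If sites differ in the date they record, patients with the same treatment course would be allocated differently.

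**Working it through.** **Text check.** Nothing in SAP 5.4.2, 5.4.2.1, 5.4.2.2 or 6.6.1.4 removes taper doses from the prophylactic regimen. SAP 5.4.8 defines an ITI period from the first ITI dose to study completion or withdrawal, which contains the taper. SAP 6.6.1.5 uses that period to exclude data from the last-prescribed-dose table. SAP 6.6.1.4 does not use it.

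**Illustration for one patient.** The plan gives no figure to reproduce, and the taper schedule is redacted in both documents. These inputs are therefore assumptions unless a source is given:

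- taper of 84 days (the 12-week minimum in SAP 7.4.9);
- mean taper dose *m* of 50, 100 or 150 IU/kg/day (an even step-down from 200 to 12.5 would average (200 + 12.5)/2 = 106);
- 274 days of relapse monitoring (9 months, SAP 7.4.9) plus 60 days of prophylaxis before ITI, 334 days in all;
- prophylaxis at 50 IU/kg every 4 days, or 12.5 IU/kg/day (inside the protocol's range).

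Formula (SAP 6.6.1.4): total IU/kg ÷ efficacy-period days × 365.25.

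Taper kept out: 12.5 × 365.25 = 4,566 IU/kg/year.

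Taper counted as prophylaxis: (84 × *m* + 334 × 12.5) ÷ 418 × 365.25.

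| *m* | IU/kg/year | Ratio to 4,566 | Mean weekly dose (IU/kg) |
|---|---|---|---|
| 50 | 7,318 | 1.60 | 140.3 |
| 100 | 10,988 | 2.41 | 210.6 |
| 150 | 14,658 | 3.21 | 280.9 |

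Without the taper the weekly dose is 12.5 × 7 = 87.5 IU/kg. The weekly-dose column applies only if taper injections are coded as prophylactic, because SAP 6.6.1.3 works from consecutive prophylactic doses.

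Sensitivity of the ratio:

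- 30 to 180 days of earlier prophylaxis: 1.5 to 3.4;
- 65 IU/kg every 3 days as the base regimen: 1.3 to 2.2;
- 25 IU/kg every 5 days to 80 IU/kg every 3 days, with 0 to 180 days of earlier prophylaxis: 1.1 to 7.8.

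**Cohort mean.** With *k* affected among 90 (both assumed) and the others averaging 4,566, the mean rises by (*k*/90) × (ratio − 1):

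| *k* | *m* = 50 | *m* = 100 | *m* = 150 |
|---|---|---|---|
| 2 | 1.3% | 3.1% | 4.9% |
| 5 | 3.3% | 7.8% | 12.3% |
| 10 | 6.7% | 15.6% | 24.6% |

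**SD and median.** With *s* the SD without the taper (assumed 1,000 to 1,500), *p* = *k*/90 and δ the patient's excess, the SD ratio is about √(*s*² + *p*(1 − *p*)δ²)/*s*:

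- *k* = 2, *m* = 50, *s* = 1,500: 1.04;
- *k* = 5, *m* = 100, *s* = 1,000: 1.78;
- *k* = 10, *m* = 150, *s* = 1,000: 3.3.

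The median moves by about 1 to 5%.

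**Taper placed in ITI instead.** After 12 months of ITI, a patient's mean daily dose is (200 × 365 + 84 × *m*)/449. That is 14.0%, 9.3% or 4.7% below 200 for *m* = 50, 100 or 150. If half of the ITI patients taper (assumed), the ITI group mean at *m* = 50 falls by about 14.0/2 = 7%, against a 1.3% rise in the prophylaxis mean with two affected patients of 90.

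**The case against.** The strongest reply is that the word in brackets merely names the transition, echoing the heading of Protocol 10.2.7.5, and that the rule turns on the eCRF change day. Read with 3.1.2.3, 3.1.3 and 3.1.5.3, that day could be the reversion after the taper, and taper doses would stay in ITI. This stands as a possible reading. A reader might infer that taper doses will certainly enter prophylaxis consumption; the documents do not support that. But the alternative reading leaves the label unexplained and the date undefined, so the conflict remains.

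The phrase "between the start of tapering through the beginning of prophylaxis" in SAP 7.4.9 might be taken as a regimen boundary. It governs when relapse tests are repeated, so it is only weak support for the sequence.

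Clean figures are partly planned already. The inhibitor-subgroup tables include a column of patients without an inhibitor, and SAP 5.4.7 splits inhibitor patients' data at the inhibitor date. Protocol 16.2.1 also calls for data after the last negative test to be summarized separately. However, SAP 5.1.1.1 defines the by-regimen groups by time on regimen without that split, and 5.1.1.2 ties it to the inhibitor sub-classification presentation.

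The numbers affected are probably small. Under Protocol 10.2.7.4.2 and SAP 7.4.9 only complete successes taper (SAP 5.1.2.2 is looser, adding those who complete 33 months), and end of study cuts off patients still in follow-up. That limits the weight of the point without removing it.

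**Conclusion.** The SAP contradicts itself on where the post-ITI taper belongs. Its operative rule, read as labelled, puts taper doses into by-regimen prophylaxis consumption and taper time into the by-regimen bleeding-rate and adverse-event columns. At best, allocation depends on the date each site records. This should be corrected before analysis.

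The size is illustrative only. With taper doses redacted and patient numbers assumed, the rise in the mean runs from about 1% to 25%. The top of that range needs ten tapering patients averaging 150 IU/kg/day throughout. What holds more generally is the pattern: mean, SD and maximum move more than the median. The effect on average weekly dose is conditional on how taper injections are coded.

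A reader might infer that the trial's main result is at risk. It is not: the primary endpoint, overall consumption and the no-inhibitor column do not use this boundary, and no hypothesis is tested.

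A reader might also infer that moving the taper into ITI distorts less. That can hold for an individual patient, but it is not shown for the group. The ITI group is small, and the shift in its mean could be as large or larger.

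**What to change.** In SAP 5.2.3, end the ITI regimen at the last full ITI dose. Start post-ITI prophylaxis at the first regular prophylactic dose after the last taper dose. Name the eCRF date that marks each boundary. Show taper time in its own row of the by-regimen consumption, average-dose, ABR and AE tables. Bring SAP 3.1.3, which treats both tapering and monitoring as part of the ITI regimen, into line.

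The cost is one boundary rule, a little programming and one extra table row. The dates and doses are already collected, and patients have nothing more to do.
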